SAM clinic Intervention: See Figure 3 for depiction of SAM clinic visit process. Typically 8-10 patients are scheduled in SAM clinic, during which a sleep provider led team comprised of either a sleep clinician or sleep nurse practitioner along with DME representative(s). Each session begins with a discussion about OSA and PAP. The provider interacts with each patient personally. This occurs on weekly basis at main and other selected regional locations of CC. Various modes of trouble shooting of PAP related issues are tailored to solve PAP adherence issues including

mask complaints, nasal issues, pressure intolerance, anxiety, and other related barriers to PAP adherence. Different interface masks might be provided during the visit depending on the clinical situation (e.g those with claustrophobia will be given nasal pillows). When the provider is seeing patients individually other patients have the opportunity to interact and offer informal interpersonal support to other participants in dealing with similar PAP related issues. The provider makes an individualized follow-up plan for each patient, which may include another SAM visit or referral back to the non-sleep provider.

Usual Care: The control arm will receive usual routine care. Patients will follow-up only with their provider for the monitoring of PAP adherence issues. The follow up visit is usually scheduled1-3 months of the PAP set up and further follow up is contingent upon the clinical scenario of the patient. The usual arm care patients will be recommended to make a follow up appointment with their provider by the research coordinator, if not already scheduled.

Data Collection: Data related to PAP barrier questionnaire, PAP adherence, BAS-FS personality index, physiological measurements, PROs (mentioned below) will be collected and entered into the REDcap database of Cleveland Clinic (secured database).

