Data Analysis Plan: Patients will be randomized 1:1 to the two treatment groups using a blocked randomization that stratifies patients based on OSA severity (AHI, RDI, REI 5-15 vs.15-30, 30+). Blocks will be of random size blinded from study investigators. Only the intent-to-treat population will be included in primary analyses, while secondary analyses will be performed in the per-protocol population defined by participation in the SAM Clinic for the treated group versus usual care patients. Linear and non-linear mixed effect models will be used to compare groups for changes in PAP adherence (primary endpoint), PROs, and barriers over time. In these models, group by time interactions will be used to evaluate trend differences between groups, and mean differences primarily at 3 months and secondarily at 1 month. The use of mixed effect models will account for loss to follow-up under the assumption that such dropout is missing at random, though this assumption will be evaluated graphically. If data are missing not at random, pattern mixture models will be further explored to evaluate group differences. Analyses will be performed assuming an overall significance level of 0.05, and comparisons of mean differences at 1 and 3 months will each use a 0.05 significance level. Statistical support will be provided by a biostatistician within the Cleveland Clinic Department of Quantitative Health Sciences for this project.

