Sample Size: Sample size calculations were performed based on detecting mean differences in PAP adherence at 1 and 3 months. In this study, patients undergoing motivational enhancement (ME) showed an average PAP adherence of 264 minutes (SD: 174) as compared to average PAP adherence of 198 (SD: 168) among those without ME. Given the overall paucity of data addressing PAP adherence in a group setting-we utilized this data from RCT with ME given the similarities in approach. If we assume a similar effect size, and assume that average adherence will be log-normally distributed with a coefficient of variation of 0.65, there will be 80% power to detect an increase of 33% in the mean average nightly PAP adherence with 67 patients per group. Allowing for non-participation and non-compliance rates of 10% in each group, a total of 83 patients per group will be enrolled, the adjustment described by Lachin. This sample size will also provide similar power to detect moderate effect size differences between study groups on PROs, even allowing for dropout on these measures of up to 20% on these measures. Power calculations were performed using SAS software (version 9.4; Cary, NC) and assumed use of a two-sided test with significance levels of 0.05.

Limitations/Pitfalls and Alternative Strategies: Since this is a comparative study comparing the effectiveness of SAM clinic to usual standard of care by providers, there are inherent limitations to such a design. There is a possibility of cross over for the patients. We have accounted for possible cross-contamination in the statistical design by increasing the sample size. Patient without email access will be sent paper format of questionnaire. If recruitment become a challenge, will target recruitment efforts in primary care clinics. This study may not be able to shed the light on effectiveness specific mechanisms of SAM clinic intervention e.g. group component vs sleep provider interaction or more. Further research will be needed to investigate it.

Adverse Event Reporting: Reporting of adverse events will follow standard reporting guidelines. Each event will be classified according to its severity, whether it was expected or unexpected, and its likelihood of relatedness to the study and reviewed by the study medical monitor, [name].

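### SAM care is shared by session, provider and location, but the plan neither allows for, models nor records that clustering, so the interval may be somewhat too narrow

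*Combined protocol and SAP*

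**What the plan says.** The Data Analysis Plan randomizes single patients: "Patients will be randomized 1:1 to the two treatment groups using a blocked randomization". Under SAM clinic Intervention, care is given in sessions: "Typically 8-10 patients are scheduled in SAM clinic". A session has one team, led by a sleep clinician or a sleep nurse practitioner together with equipment staff. It opens with a joint discussion, and patients can support one another while the provider sees each of them in turn. On frequency and place the section says "This occurs on weekly basis at main and other selected regional locations of CC". Control patients follow up only with their own provider.

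For the analysis, "Linear and non-linear mixed effect models will be used to compare groups for changes in PAP adherence (primary endpoint") and for the other outcomes. Group-by-time interactions carry the comparison, and the stated reason for mixed models is loss to follow-up. The random effects are not specified, and no session, provider or location term is named.

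The Sample Size section states that "there will be 80% power to detect an increase of 33% in the mean average nightly PAP adherence with 67 patients per group". The increase to 83 per group is for non-participation and non-compliance, and the Limitations section attributes the increase to crossover. Data Collection lists adherence, barriers, a personality index, physiological measurements and patient-reported outcomes. It does not list session, provider or location.

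**The concern.** This is a partially nested design: one arm shares its treatment sources and the other is treated patient by patient. If some SAM providers obtain better adherence than others, outcomes of patients with the same provider are correlated. An analysis that takes all patients as independent then understates the standard error of the SAM mean, and so of the treatment difference. The interval is too narrow and the test rejects too often.

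The protocol gives two reasons to take this seriously. The Limitations section itself names the group component and the interaction with a sleep provider as possible mechanisms. The Significance section wants the effect sizes to inform multi-center trials, that is, to carry over to other providers. Without the identifiers among the trial data, the question cannot be examined afterwards from the items listed.

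**Working it through.** **1. The plan's own sample size**

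Inputs from Sample Size: "average PAP adherence of 264 minutes (SD: 174) as compared to average PAP adherence of 198 (SD: 168"); "assume that average adherence will be log-normally distributed with a coefficient of variation of 0.65"; "assumed use of a two-sided test with significance levels of 0.05"; 80% power.

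- Effect on the log scale: δ = ln(264/198) = 0.2877.
- SD on the log scale: σ = √ln(1 + 0.65²) = 0.5936.
- n per group = 2[σ(1.960 + 0.842)/δ]² = 66.8, so 67.
- Inflation: 67/0.9² = 82.7, so 83.

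Both figures reproduce from formulas for independent patients. Nothing is left over for a design effect.

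**2. Formulas for clustering in the SAM arm only**

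With m trial patients per cluster:

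- SAM-arm design effect: DE = 1 + (m − 1) × ICC.
- True SE of the difference over the naive SE: r = √[(DE + 1)/2].
- Type I error of the uncorrected test: 2[1 − Φ(1.960/r)].
- Power of the same uncorrected test: Φ[(δ/SE₀ − 1.960)/r], where SE₀ = σ√(2/n). At n = 67, SE₀ = 0.1026, δ/SE₀ = 2.805, and power is Φ(0.845/r).

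Correlation in the usual-care arm is set to zero. The ICC is an assumption throughout.

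**3. Session level**

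Table 3 plans 16 + 16 + 17 + 17 + 17 = 83 patients per arm over five quarters, about 65 weeks. That is 83/65 = 1.28 SAM patients a week over all locations. With Poisson session counts, the size-weighted mean cluster is 1 + λ.

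- All at one location: λ = 1.28, cluster 2.28, DE at ICC 0.05 = 1.064, r = 1.016.
- Spread over three locations (assumed): λ = 0.43, cluster 1.43, DE = 1.021, r = 1.005.

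The standard error changes by about 0.5% to 1.6%, which is negligible.

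**4. Provider level**

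The number of providers k is not given; 3 to 12 is assumed, sharing patients equally. Type I error uses the 83 enrolled (m = 83/k). Power uses the 67 for which the plan claims 80% (m = 67/k). Both columns describe the same uncorrected test.

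| k | ICC | DE (83) | r (83) | Type I error (83) | Power (67) |
|---|---|---|---|---|---|
| 3 | 0.01 | 1.27 | 1.065 | 0.066 | 0.789 |
| 3 | 0.05 | 2.33 | 1.291 | 0.129 | 0.753 |
| 5 | 0.01 | 1.16 | 1.038 | 0.059 | 0.794 |
| 5 | 0.05 | 1.78 | 1.179 | 0.096 | 0.770 |
| 8 | 0.01 | 1.09 | 1.023 | 0.055 | 0.797 |
| 8 | 0.05 | 1.47 | 1.111 | 0.078 | 0.781 |
| 12 | 0.01 | 1.06 | 1.015 | 0.053 | 0.798 |
| 12 | 0.05 | 1.30 | 1.071 | 0.067 | 0.788 |

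**5. What a correction with few providers costs**

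Satterthwaite degrees of freedom are about (DE + 1)²/[DE²/(k − 1) + 1/(n − 1)]. For k = 3, ICC 0.05 and n = 83: 3.333²/(2.333²/2 + 1/82) = 4.1. The interval is then about 1.8 times as wide as the naive one, and power is about 46%. With n = 67 the figures are about 1.7 times and 43%.

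**The case against.** The strongest objection is that most of the size rests on facts the documents do not contain. A reader might infer that the same few teams run the sessions week after week. SAM clinic Intervention gives only the team's make-up, the weekly frequency and the several locations; it is silent on rotation and on how many providers there are. That stands, so the provider figures are conditional.

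A reader might also take 8 to 10 as the cluster size. That is clinic attendance, not trial patients per session, and Table 3 accrual does not support it.

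Nor do the documents show that the model assumes independence between patients of the same provider. The random effects are unspecified, and only the omission of such a term can be stated. For the sample size, by contrast, independence is shown by reproduction.

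It is tempting to pair a type I error of 0.13 with power of 62%. The 62% (k = 3, ICC 0.05, 67 per arm) belongs to a test using the enlarged standard error, and the 0.13 to the uncorrected test. No single test has both.

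Location needs care as well. Since individuals are randomized, differences in prognosis between locations affect both arms and do not by themselves inflate the type I error; only variation in the SAM effect does. Usual-care patients may also cluster by their own provider.

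Finally, treating one health system's providers as fixed is defensible, and a provider random effect with very few providers is costly. This stands against making the correction the primary analysis. It does not stand against recording the identifiers and running a sensitivity analysis.

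**Conclusion.** The point holds in a limited form. The sample size has no design effect, the analysis plan names no session, provider or location term, and the listed data would not allow a later check. Session clustering can be set aside. Provider clustering could matter if few providers treat most SAM patients and their results differ. Under the assumed grid (3 to 12 providers, ICC 0.01 to 0.05, equal shares, no correlation in usual care), type I error runs from about 0.053 to 0.13. Power of the planned test falls little, to between 75% and 80% at 67 per arm. The upper end is one corner of that grid, not an estimate. The type I figures describe an average SAM effect of zero with real differences between providers; if SAM changed nothing for anyone, it would induce no clustering of this kind. Confidence in the size is low, and the point is a desirable improvement, not a reason to doubt the design.

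**What to change.** - Add three REDCap fields for each SAM visit: session, lead provider and location.
- State how they map to clusters: a patient with repeat visits is classified by the first SAM visit, and each SAM-arm non-attender counts as an own cluster, so that the intent-to-treat population stays complete.
- Keep the planned model as primary. Pre-specify one sensitivity analysis with a provider random effect in the SAM arm only, small-sample degrees of freedom, and location adjusted for in both arms.
- Report the ICC, and qualify the conclusion if the two analyses disagree.

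The cost is three fields and one extra model, with no change to enrollment or care. With few providers, the variance component will be imprecise and the sensitivity interval noticeably wider, as step 5 of the working shows. That is the reason for not making it primary.

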Eligibility criteria: Inclusion Criteria: 1) ≥18 years old 2) Moderate to severe OSA (apnea hypopnea index (AHI), respiratory disturbance index (RDI), Respiratory Event Index (REI)≥5 events/hr) on polysomnogram (PSG) or home sleep apnea testing (HSAT) 3) Followed by non-sleep and sleep providers for OSA 4) New PAP set up < 1 month 5) Sub-optimal PAP adherence by objective PAP adherence data (≤70 % usage and ≤4 hours of average PAP usage) Exclusion criteria: 1) Central sleep apnea (≥50% apneas are central) and/or presence of Cheyne-Stokes breathing 2) Pregnant women 3) Patients on supplemental oxygen 4) Patients not able to attend SAM clinic 5) Inability to provide informed consent

Randomization: Patients will be randomized 1:1 to SAM clinic/sleep hygiene or usual care/sleep hygiene (care by non-sleep providers) using a blocked randomization that stratifies patients based on OSA severity (AHI, RDI, REI 5-14.9, 15-29.9 vs. AHI, RDI, REI >30+). Random assignments to the three arms will be made

with the use of a randomization database in REDcap.

Study Protocol: All data from PAP devices set up by CCDME will be downloaded via wireless communication or smartcard. PAP adherence will be monitored by the research coordinator before randomization (randomized to SAM Clinic or usual care with their provider) and after 1 and 3 month of either intervention. A sample size of approximately 83 subjects is estimated in each group over a period of 2 years (total n=166). SAM clinic appointment will be offered within 1-2 weeks of patient consent and randomization into that group. Both groups will be provided with PAP barriers questionnaires which will be administered in "yes/no" format focused upon specific mask issues (air leak, irritation, fitting problems, type of mask) and other issues (nasal congestion, claustrophobia etc.) and the same questionnaires will be instituted in both the groups at the 1- and 3-month follow-up through the email using redcap platform. See Figure 2 for the flow diagram of the study.

[figure not shown]
[figure not shown]

Figure 2: Flow Diagram of Study

Sleep Hygiene Education: A research coordinator will provide both the arms with sleep hygiene education material at baseline that entails regularization of sleep wake schedule, stimulus control education, adequate amount of sleep and comfortable environment conducive to sleep (by mail).

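### The Data Analysis Plan does not say how baseline PAP adherence or the OSA-severity strata enter the primary model; stating an adjusted 3-month contrast costs about 3 df and may gain precision

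*Combined protocol and SAP*

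**What the plan says.** The Data Analysis Plan is the only description of the primary model. It states that "Linear and non-linear mixed effect models will be used to compare groups for changes in PAP adherence (primary endpoint), PROs, and barriers over time". Group-by-time interactions are to be used, and the comparison concerns "mean differences primarily at 3 months and secondarily at 1 month". No covariate is named there or elsewhere. Specific Aim 1 likewise speaks of change from baseline, without saying how baseline is used.

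Both candidate covariates are available without new data:

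- **Baseline adherence.** Under Study Protocol, "PAP adherence will be monitored by the research coordinator before randomization". Entry limits its range, since the inclusion criteria require "Sub-optimal PAP adherence by objective PAP adherence data (≤70 % usage and ≤4 hours of average PAP usage".
- **OSA severity.** The Randomization paragraph "stratifies patients based on OSA severity (AHI, RDI, REI 5-14.9, 15-29.9 vs. AHI, RDI, REI >30" and above. The Data Analysis Plan describes a "blocked randomization that stratifies patients based on OSA severity (AHI, RDI, REI 5-15 vs.15-30, 30" and above. The cut-points are not written the same way in the two places.

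The Sample Size section takes its effect from an earlier trial with "average PAP adherence of 264 minutes (SD: 174) as compared to average PAP adherence of 198 (SD: 168". It goes on to "assume that average adherence will be log-normally distributed with a coefficient of variation of 0.65", and arrives at 67 per group for 80% power, inflated to 83.

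**The concern.** Two analysts who followed this text faithfully could report different primary estimates from the same data. One might subtract baseline. Another might fit baseline, 1 month and 3 months as responses with free arm means. That second model returns either the plain 3-month difference or the difference in change, depending on which contrast is taken. A third might adjust for baseline.

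Randomization makes all of these unbiased for the same difference on a given scale, so the stake is not bias. Two things are at risk: precision, in a trial sized at 80% with little to spare, and an analysis choice that could be made after the results are seen. The strata raise a smaller version of the same question. If severity predicts adherence, stratifying on it and then leaving it out of the model makes the test slightly conservative.

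**Working it through.** **Inputs.** From the Sample Size section: means 264 and 198 minutes, log-normal adherence, CV 0.65, 67 per group, two-sided 0.05. Assumed, because the documents do not give them: r, the correlation between baseline and 3-month adherence among enrolled patients; k, baseline SD divided by 3-month SD; and R², the share of variance explained by severity.

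**Step 1: reproduce the plan's figure.**

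- Log-scale SD = √ln(1 + 0.65²) = 0.5936. Effect = ln(264/198) = 0.2877.
- n per group = 2 × [0.5936 × (1.960 + 0.842) / 0.2877]² = 66.8, so 67.
- Inflation: 67 / (1 − 0.10)² = 82.7, so 83.

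Both stated figures reproduce. The full marginal SD was used, so they describe an unadjusted log-scale comparison. Power at 67 is 80.1% by the normal approximation and 79.5% by noncentral t (df 132). The t-based figure is used below.

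**Step 2: relative variance of each contrast** (plain 3-month = 1).

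- Change score: 1 + k² − 2rk
- Baseline-adjusted: 1 − r²

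Change minus adjusted is (1 + k² − 2rk) − (1 − r²) = (k − r)², which is never negative. Plain minus adjusted is r², also never negative. Apart from degrees of freedom, adjustment cannot lose to either. It ties with the change score when k = r and with the plain contrast when r = 0.

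**Step 3: cost.** Baseline uses 1 df and severity 2. With 134 patients the full variance charge is (134 − 3)/(134 − 6) = 1.0234, or 1.2% in SE. Break-even against the plain contrast with a non-prognostic stratum is r = √(1 − 1/1.0234) = 0.15. The full charge is on the pessimistic side: in a simulation of 8,000 trials at r = 0, the SD of the estimate rose from 0.1035 to 0.1038, or 0.3%.

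**Step 4: power at 67 per group** (SE = 0.5936 × √(2/67) = 0.1026 times the root of the relative variance; df 129 when adjusted).

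| r (assumed) | Plain 3-month | Adjusted | Adjusted, full cost | Change, k = 1 | Change, k = 0.5 |
|---|---|---|---|---|---|
| 0.1 | 79.5% | 79.9% | 79.0% | – | – |
| 0.2 | 79.5% | 81.1% | 80.2% | 59.5% | 77.6% |
| 0.3 | 79.5% | 83.1% | 82.2% | 65.3% | 81.5% |
| 0.5 | 79.5% | 89.5% | 88.8% | 79.5% | 89.5% |

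**Step 5: equivalence of the constrained model.** On one simulated complete data set, a model with baseline as a response and a common baseline mean gave 0.17779, identical to covariate adjustment. The plain difference was 0.205 and the change difference 0.164. The common-mean constraint is what brings the gain, and the plan does not state it.

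**Step 6: omitted strata.** At an assumed R² of 5%, the reported SE is too large by 1/√0.95 = 1.026. The true type I error is then 2 × [1 − Φ(1.96 × 1.026)] = 0.044 instead of 0.05.

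**Step 7: what a log-scale contrast estimates.** It back-transforms to a ratio of geometric means. Under log-normality the source trial's figures give log variances ln(1 + (174/264)²) = 0.361 and ln(1 + (168/198)²) = 0.542, that is, log SDs of 0.60 and 0.74. The geometric ratio is 1.333 × exp[(0.542 − 0.361)/2] = 1.46, against a ratio of means of 1.33. The two agree only when the log variances are equal across arms.

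**The case against.** The plan already fixes the intention-to-treat population, the model class, the group-by-time terms and the 3-month priority. Its change wording suggests that baseline enters in some way, perhaps as a response. If the arms then share a common baseline mean, most of the gain is already there. This stands: the defensible claim is that the form of use is unstated, not that baseline is ignored.

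The gain is also not assured. No correlation appears in the documents, the entry cap narrows the baseline range and may lower r, and at r = 0.1 with the full cost charged the adjusted power (79.0%) is just under the plain 79.5%. That stands too. Against change scores, the gain vanishes when k is close to r.

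Three stronger readings are tempting, and the documents support none of them:

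- A reader might infer that the trial is underpowered, from the 59.5% and 65.3% for change scores. The plan does not commit to a change score, and those figures need k = 1 and a low r, neither of which is documented.
- A reader might infer that enrolment could be cut because adjustment adds power. That would rest on an assumed r.
- A reader might use the source trial's SDs in minutes to argue that a raw-minutes analysis loses much power through scale alone. Those SDs imply CVs of 174/264 = 0.66 and 168/198 = 0.85, not 0.65 in both arms, so the comparison mixes a different variance assumption with the change of scale.

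**Conclusion.** The point holds as one of efficiency and pre-specification. The plan leaves open how baseline adherence and the severity strata enter the primary model, and every form its wording permits is at best as precise as the adjusted contrast, apart from about 3 df. Over the plain 3-month contrast, the gain runs from nil or slightly negative below about r = 0.15 (with a non-prognostic stratum) to about 10 points at r = 0.5 (79.5% to 89.5%). Over change scores with equal SDs it is larger: about 22 points at r = 0.2 and 10 at r = 0.5. All of this rests on assumed r and k. Most of any gain would come from baseline adherence; the severity term mainly aligns the analysis with the randomization.

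Nothing here makes the planned analysis invalid. Omitting the strata errs on the conservative side, and 67 evaluable and 83 enrolled per group remain correct for an unadjusted log-scale comparison.

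**What to change.** First reconcile the severity cut-points between the Randomization paragraph and the Data Analysis Plan, so that values at 15 and 30 belong to one stratum only. Then state in the Data Analysis Plan:

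- The primary contrast is the 3-month between-arm difference in average nightly PAP use, on a named scale.
- It comes from a linear mixed model of 1- and 3-month adherence with visit, arm-by-visit, baseline adherence (same scale)-by-visit, the three-level severity stratum as a fixed effect, and unstructured within-patient covariance.
- A model with baseline as a response is an equivalent alternative only if a common baseline mean across arms is stated. Choose one form, and do not enter baseline as both response and covariate.
- If the log scale of the Sample Size section is used, the result is a ratio of geometric means, with a rule for zero use, because the log of zero is undefined.

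The covariate also needs one defined pre-randomization download window, since the Study Timeline puts the compliance recheck at week 4 and randomization in weeks 4–8.

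The cost is wording, about 3 df and at most about 1.2% in SE. No new data are needed, and the sample size should not change.

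### The missing-not-at-random analysis runs only if the data are judged missing not at random, which the one named check, a graphical one, cannot establish

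*Combined protocol and SAP*

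**What the plan says.** In the combined protocol and SAP, the Data Analysis Plan states: "Linear and non-linear mixed effect models will be used to compare groups for changes in PAP adherence (primary endpoint), PROs, and barriers over time". Within these models the group comparison concerns "mean differences primarily at 3 months and secondarily at 1 month". Loss to follow-up is handled "under the assumption that such dropout is missing at random, though this assumption will be evaluated graphically". The next step is conditional: "If data are missing not at random, pattern mixture models will be further explored to evaluate group differences".

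The plan names no particular plot, criterion or decision rule. It gives no dropout patterns, identifying restrictions or delta values for the pattern mixture models. No unconditional MNAR analysis appears elsewhere in the document.

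Two other places bear on the size of the problem. Under Study Protocol, the primary data come from the machine: "All data from PAP devices set up by CCDME will be downloaded via wireless communication or smartcard". Under Sample Size, the plan allows up to 20% dropout on the patient-reported outcomes (PROs). It gives no expected rate of missing 3-month device data.

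**The concern.** MAR and MNAR differ only in how the unobserved values are distributed given the observed ones. Plots can show that dropout is related to earlier adherence, which is evidence against missing completely at random. They cannot show whether, given that earlier adherence, the unseen 3-month values follow the model. The document does not say that the plot alone triggers the pattern mixture analysis, but it names no other check. Whether to run that analysis, and how to set it up, would therefore be decided after the data are seen.

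If unobserved patients depart from the MAR prediction, and do so differently by arm, the 3-month difference shifts, in either direction. No planned analysis is certain to show by how much. The same model family serves the PROs, which depend on returned questionnaires and are more exposed. The sample-size allowances protect power; they do not protect against bias from informative dropout.

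**Working it through.** **Inputs.** From Sample Size: mean use 264 minutes (SD 174) against 198 (SD 168); log-normal with CV 0.65; 80% power; two-sided 0.05; 67 per group raised to 83 for 10% non-participation and non-compliance; up to 20% dropout on PROs. The missing rates for device data (5%, 10%, 20%) and all shifts are assumptions. Calculations use a normal approximation to an unadjusted 3-month comparison.

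**The plan's own figure.** Log SD = √ln(1 + 0.65²) = 0.594; log ratio = ln(264/198) = 0.2877. n = 2 × (1.96 + 0.84)² × 0.594² / 0.2877² ≈ 67 per group, and 67/0.9² = 82.7, so 83. The stated sample size reproduces and is not in question.

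**Primary endpoint, only missing SAM patients depart from MAR.** Let q be the missing share in each arm. SE = 0.594 × √(2/(83(1 − q))). If missing SAM patients use half what MAR predicts, the log ratio is 0.2877 + q × ln 0.5. Significance is lost at a log shift of (0.2877 − 1.96 SE)/q.

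| q | SE | z under MAR | Ratio after halving | z | p | Reduction at which significance is lost |
|---|---|---|---|---|---|---|
| 5% | 0.0945 | 3.04 | 1.29 | 2.68 | 0.007 | 87% |
| 10% | 0.0971 | 2.96 | 1.24 | 2.25 | 0.025 | 62% |
| 20% | 0.1030 | 2.79 | 1.16 | 1.45 | 0.148 | 35% |

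The last column is 1 − exp(−shift), with shifts of 2.05, 0.973 and 0.429. Treating q as random adds (ln 0.5)² × q(1 − q)/83 to the variance and lowers z to 2.19 at 10% and 1.39 at 20%.

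**Primary endpoint, halving in both arms.** Log ratio = 0.2877 + (q_SAM − q_UC) × ln 0.5. At equal rates the ratio stays at 1.33. With 20% missing in SAM and 10% in usual care it is 1.24 (z 2.18); with 10% and 20% it is 1.43 (z 3.57).

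**Extreme case, missing set to zero use.** Zero has no logarithm, so this is on raw minutes. Difference = (1 − q_S) × 264 − (1 − q_U) × 198. Variance per arm = (1 − q)s² + q(1 − q)m², and SE = √(sum/83).

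| SDs | 8 of 83 usual-care patients missing | Equal numbers missing |
|---|---|---|
| 174 and 168 | 9 SAM missing: p = 0.040; 10: p = 0.053 | 14 each: p = 0.048; 15 each: p = 0.052 |
| 171.6 and 128.7 (CV 0.65) | 11 SAM missing: p = 0.045; 12: p = 0.061 | 19 each: p = 0.047; 20 each: p = 0.051 |

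**PROs at the plan's 20% dropout.** 83 × 0.8 ≈ 66 per arm; SE = √(2/66) = 0.174 SD. The effect detectable with 80% power is 2.80 × 0.174 = 0.488 SD. If SAM dropouts alone score 0.5 SD worse than MAR predicts, the effect is 0.488 − 0.2 × 0.5 = 0.388 SD (z 2.23, p = 0.026). At 1 SD worse it is 0.288 SD (z 1.65, p = 0.098). Significance is lost at (0.488 − 0.341)/0.2 = 0.73 SD worse. For MAR effects of 0.4 and 0.6 SD the corresponding shifts are 0.29 and 1.29 SD.

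**The case against.** The strongest reply is that for the primary endpoint the problem is largely hypothetical. Device data are collected in both arms independently of questionnaire return, so the usual route to MNAR, non-users disappearing from view, is mostly closed. This stands as a limit on weight. It does not remove the point: the document does not say downloads will be complete, smartcard retrieval is one of the two routes, and the plan itself provides for loss to follow-up.

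Second, shifting only the SAM arm is adverse by design, and nothing in the documents supports that asymmetry. Even then, halving leaves significance intact at 5% and 10% missing. With equal missing rates and the same proportional shift in both arms the ratio does not move. With equal numbers set to zero it takes 15 or 20 of 83 per arm (18% or 24%) to lose significance. This also stands: the primary conclusion would be fairly robust under many scenarios.

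Third, the planned mixed models use repeated measures and would normally have a smaller SE, moving the tipping points outward. The documents give no correlation, so this cannot be quantified, and the thresholds above are not the trial's own.

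Finally, the plan already recognises MNAR and names a suitable class of model. That is to its credit, but the commitment depends on a condition that observed data cannot establish.

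**Conclusion.** The concern holds. The stated rule has no workable trigger, so robustness of the 3-month contrast to an untestable assumption is not certain to be reported. The MAR mixed model itself can stand as the primary analysis.

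The practical weight is modest for device-recorded adherence and greater for the PROs, where the plan's own 20% dropout puts the tipping shift at 0.73 SD in one arm for an effect of 0.49 SD. That figure is sensitive to the true effect. The primary-endpoint figures depend on assumed missing rates and on how far missing patients depart from MAR in each arm. They show that the result can change, not that it will.

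**What to change.** Keep the plots as description only. Pre-specify a delta-adjusted pattern-mixture (tipping-point) analysis of the 3-month primary contrast, and report it beside the primary result whatever the plots show. Let delta vary separately by arm and express it as percentage less use than MAR predicts: 0 (MAR), then for example 25%, 50% and 75%, and finally 100%, which is zero use. State the scale; the zero-use case must be computed on raw minutes. Apply the same unconditional rule to the PROs, with delta in SD units.

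The cost is SAP wording, one further result beside the primary and one line per PRO. Sample size, primary model and data collection do not change.
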